8.2 DATA QUALITY ASSURANCE

A quality assurance audit/inspection of this trial may be conducted by the sponsor, sponsor's designees, or by IRB / IEC or by regulatory authorities. The quality assurance auditor will have access to all medical records, the investigator's trial-related files and correspondence, and the informed consent documentation of this clinical trial.

8.3 RECORDS

CRFs for individual patients will be provided by the sponsor. For drug accountability, refer to Section [4.1.13](#).

8.3.1 Source documents

In accordance with regulatory requirements the investigator should prepare and maintain adequate and accurate source documents and trial records that include all observations and other data pertinent to the investigation on each trial patient. Source data as well as reported data should follow good documentation practices and be attributable, legible, contemporaneous, original and accurate. Changes to the data should be traceable (audit trail). Data reported on the CRF must be consistent with the source data or the discrepancies must be explained.

The current medical history of the patient may not be sufficient to confirm eligibility for the trial and the investigator may need to request previous medical histories and evidence of any diagnostic tests. In this case the investigator must make documented attempts to retrieve previous medical records. If this fails a verbal history from the patient, documented in their medical records, would be acceptable.

During the site visit the sponsor's Clinical Research Associate (CRA) or auditor must be granted access to the original patient file (see Section [8.3.2](#)). The investigator must ensure that all patient identifiers (e.g. patient's name, initials, address, phone number, social security

Proprietary confidential information © 2021 Boehringer Ingelheim International GmbH or one or more of its affiliated companies

number) have properly been removed or redacted from any copy of the patients' source documents before sending them to the sponsor.

If the patient is not compliant with the protocol, any corrective action e.g. re-training must be documented in the patient file.

For the CRF, data must be derived from source documents, for example:

- Patient identification: gender, date or year of birth (in accordance with local laws and regulations)
- Patient participation in the trial (substance, trial number, patient number, date patient was informed)
- Dates of patient's visits, including dispensing of trial medication
- Medical history (including trial indication and concomitant diseases, if applicable)
- Medication history
- Adverse events and outcome events (onset date [mandatory], and end date [if available])
- Serious adverse events (onset date [mandatory], and end date [if available])
- Concomitant therapy (start date, changes)
- Originals or copies of laboratory results and other imaging or testing results, with proper documented medical evaluation (in validated electronic format, if available)
- Completion of patient's participation in the trial (end date; in case of premature discontinuation document the reason for it).
- Prior to allocation of a patient to a treatment into a clinical trial, there must be documented evidence in the source data (e.g. medical records) that the trial participant meets all inclusion criteria and does not meet any exclusion criteria. The absence of records (either medical records, verbal documented feedback of the patient or testing conducted specific for a protocol) to support inclusion/exclusion criteria does not make the patient eligible for the clinical trial.
- Technical information collected on PK sampling days (e.g., PK sampling times, repeated vital signs linked with PK) may be collected on specific paper PK logs, which will be considered as source data for related entries in eCRF and are considered part of the ISF.

8.3.2 Direct access to source data and documents

The sponsor will monitor the conduct of the trial by regular on-site monitoring visits and in-house data quality review. The frequency of site monitoring will be determined by assessing all characteristics of the trial, including its nature, objective, methodology and the degree of any deviations of the intervention from normal clinical practice.

The investigator/institution will allow site trial-related monitoring, audits, IRB/IEC review and regulatory inspections. Direct access must be provided to the CRF and all source documents/data, including progress notes, copies of laboratory and medical test results, which must be available at all times for review by the CRA, auditor and regulatory inspector (e.g. FDA). They may review all CRFs and informed consents. The accuracy of the data will be verified by direct comparison with the source documents described in Section [8.3.1](#). The sponsor will also monitor compliance with the protocol and GCP.

8.3.3 Storage period of records

Trial sites:

The trial sites must retain the source and essential documents (including ISF) according to contract or the local requirements valid at the time of the end of the trial (whatever is longer).

Sponsor:

The sponsor must retain the essential documents according to the sponsor's SOPs.

8.4 EXPEDITED REPORTING OF ADVERSE EVENTS

BI is responsible to fulfil their legal and regulatory reporting obligation in accordance with regulatory requirements.

Exemptions from expedited reporting are described in Section [5.2.7.10](#), if applicable.

8.5 STATEMENT OF CONFIDENTIALITY AND PATIENT PRIVACY

Individual patient data obtained as a result of this trial is considered confidential and disclosure to third parties is prohibited with the exceptions noted below. Patient privacy will be ensured by using patient identification code numbers.

Data protection and data security measures are implemented for the collection, storage and processing of patient data in accordance with the principles 6 and 12 of the WHO GCP handbook.

Treatment data may be given to the patient's personal physician or to other appropriate medical personnel responsible for the patient's welfare. Data generated as a result of the trial need to be available for inspection on request by the participating physicians, the sponsor's representatives, by the IRB / IEC and the regulatory authorities.

8.5.1 Collection, storage and future use of biological samples and corresponding data

Measures are in place to comply with the applicable rules for the collection, storage and future use of biological samples from clinical trial participants and the corresponding data, in particular

- A Quality Management System has been implemented to ensure the adherence with the Principles of Good Clinical Practice as outlined in 'Note For Guidance On Good Clinical Practice' (CPMP/ICH/135/95)
- The BI-internal facilities storing and analysing biological samples and data from clinical trial participants as well as the laboratories' activities for clinical trials sponsored by Boehringer Ingelheim are regularly audited. The analytical groups and the banking facility are therefore assessed to be qualified for the storage and use of biological samples and data collected in clinical trials.
- Samples and data are used only if an appropriate informed consent is available.

8.6 TRIAL MILESTONES

The **start of the trial** is defined as the date when the first patient in the whole trial signs informed consent.

The **end of the trial** is defined as the date of the last visit of the last patient in the whole trial (“Last Patient Out”).

The “**Last Patient Drug Discontinuation**” (LPDD) date is defined as the date on which the last patient at an individual trial site ends trial medication (as scheduled per protocol or prematurely). Individual investigators will be notified of Suspected Unexpected Serious Adverse Reactions (SUSARs) occurring with the trial medication until 30 days after LPDD at their site.

Early termination of the trial is defined as the premature termination of the trial due to any reason before the end of the trial as specified in this protocol.

Temporary halt of the trial is defined as any unplanned interruption of the trial by the sponsor with the intention to resume it.

Suspension of the trial is defined as an interruption of the trial based on a Health Authority request.

8.7 ADMINISTRATIVE STRUCTURE OF THE TRIAL

The trial is sponsored by Boehringer Ingelheim (BI).

A Coordinating Investigator is responsible to coordinate investigators at the different sites participating in this trial. Tasks and responsibilities are defined in a contract.

The target group of Principal Investigators will be oncologists who have experiences in clinical trials of immune-oncology products and working at centres where physicians who are experts of oncology phase 1 trials are available. Tasks and responsibilities will be defined in a contract. Relevant documentation on the participating (Principal) Investigators (e.g. their curricula vitae) will be filed in the ISF. The investigators will have access to the BI clinical trial portal (Clinergize) to facilitate document exchange and maintain electronic ISF.

A Safety Monitoring Committee (SMC) will be established in this trial.

Members of the SMC will include:

- An investigator representative or delegate
- BI safety physician or delegate
- BI Team Member Medicine
- BI Project or Trial Statistician
- BI Clinical Trial Leader (CTL)

Other BI and non-BI subject matter experts may also be invited, as appropriate. The SMC documentation for this trial will define the exact membership and who should be present for decisions to be made.

The SMC will be responsible for making dose-selection decisions for BI 754091 and BI 754111, making decisions on the next cohort size, and recommending to the sponsor whether to continue, modify, or stop the trial.

The tasks and responsibilities of the SMC will be documented. The SMC will maintain written records of all its meetings.

BI has appointed a Trial Clinical Monitor, responsible for coordinating all required activities, in order to

- manage the trial in accordance with applicable regulations and internal SOPs,
- direct the clinical trial team in the preparation, conduct, and reporting of the trial,
- ensure appropriate training and information of Local Clinical Monitors (CML), Clinical Research Associates (CRAs), and investigators of participating countries.

The organisation of the trial in the participating countries will be performed by the respective local or regional BI-organisation (Operating Unit, OPU) in accordance with applicable regulations and BI SOPs, or by a Contract Research Organisation (CRO) with which the responsibilities and tasks will have been agreed and a written contract filed before initiation of the clinical trial.

Data Management and Statistical Evaluation will be done by BI according to BI SOPs.

Tasks and functions assigned in order to organise, manage, and evaluate the trial are defined according to BI SOPs. A list of responsible persons and relevant local information can be found in the ISF.

Central laboratory services, a central imaging archiving service, and an IRT vendor will be used in this trial. Details will be provided in the Central Laboratory Manual, the imaging manual, and the IRT manual available in the ISF.

10. APPENDICES

10.1 IMMUNE-RELATED ADVERSE EVENTS OF SPECIAL INTEREST

Table 10.1: 1 Immune-related adverse events of special interest

This table defines immune-related AEs that must be reported as AESIs.

Immune-related adverse events of special interest
Pneumonitis (report as AESI if an irAE is \geq Grade 2) 
• Acute interstitial pneumonitis• Interstitial lung disease• Pneumonitis
Colitis (report as AESI if an irAE is \geq Grade 2 or any grade resulting in dose modification or use of systemic steroids to treat the AE) 
• Intestinal obstruction• Colitis• Colitis microscopic• Enterocolitis• Enterocolitis haemorrhagic• Gastrointestinal perforation• Necrotizing colitis• Diarrhea
Endocrine (report as AESI if an irAE is \geq Grade 3 or \geq Grade 2 and resulting in dose modification or use of systemic steroids to treat the AE) 
• Adrenal insufficiency• Hyperthyroidism• Hypophysitis• Hypopituitarism• Hypothyroidism• Thyroid disorder• Thyroiditis• Hyperglycaemia, if \geq Grade 3 and associated with ketosis or metabolic acidosis
Endocrine (report as AESI for any grade) 
• Type 1 diabetes mellitus (if new onset)

Immune-related adverse events of special interest

Hematologic (report as AESI if an irAE is \geq Grade 3 or any grade resulting in dose modification or use of systemic steroids to treat the AE)

- Autoimmune haemolytic anaemia
- Aplastic anaemia
- Thrombotic thrombocytopenic purpura
- Idiopathic (or immune) thrombocytopenia purpura
- Disseminated intravascular coagulation
- Haemolytic-uraemic syndrome
- Any Grade 4 anaemia regardless of underlying mechanism

Hepatic (report as AESI if an irAE is \geq Grade 2, or any grade resulting in dose modification or use of systemic steroids to treat the AE)

- Hepatitis
- Autoimmune hepatitis
- Transaminase elevations (ALT and/or AST)

Infusion Reactions (report as AESI for any grade)

- Allergic reaction
- Anaphylaxis
- Cytokine release syndrome
- Serum sickness
- Infusion reactions
- Infusion-like reactions

Neurologic (report as AESI for any grade)

- Autoimmune neuropathy
- Guillain-Barre syndrome
- Demyelinating polyneuropathy
- Myasthenic syndrome

Ocular (report as AESI if an irAE is \geq Grade 2 or any grade resulting in dose modification or use of systemic steroids to treat the AE)

- Uveitis
- Iritis

Immune-related adverse events of special interest

Renal (report as AESI if an irAE is \geq Grade 2)

- Nephritis
- Nephritis autoimmune
- Renal failure
- Renal failure acute
- Creatinine elevations (report as an irAE if \geq Grade 3 or any grade resulting in dose modification or use of systemic steroids to treat the AE)

Skin (report as AESI for any grade)

- Dermatitis exfoliative
- Erythema multiforme
- Stevens-Johnson syndrome
- Toxic epidermal necrolysis

Skin (report as AESI if an irAE is \geq Grade 3)

- Pruritus
- Rash
- Rash generalized
- Rash maculopapular
- Any rash considered clinically significant in the physician's judgment

Other (report as AESI for any grade)

- Myocarditis
- Pancreatitis
- Pericarditis
- Any other Grade 3 event that is considered immune-related by the physician

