4.1.4 Dose modifications and premedications

There will be no dose reductions or escalations of BI 754091 or BI 754111 in any one patient. The dose may be delayed for up to 6 weeks because of AEs, following discussion with the sponsor.

During combination therapy, if treatment is held or discontinued due to an AE(s), both BI 754091 and BI 754111 will be held or discontinued together. If treatment is to be restarted after resolution (\leq Grade 1 or baseline – exceptions should be discussed and agreed with the sponsor) of the AE, both BI 754091 and BI 754111 must be started together.

The study drug(s) should be permanently discontinued for Grade 3 to 4 pneumonitis, Grade 3 to 4 adrenal insufficiency, Grade 4 diabetes mellitus, any grade encephalitis, Grade 4 hypophysitis, Grade 4 rash, Grade 3 to 4 colitis or recurrent colitis of any grade, any recurrent Grade 3 to 4 irAEs, transaminase increases >5 times ULN or total bilirubin >3 times ULN (unless unequivocally attributed to another cause), inability to taper steroids to 10 mg or less prednisone or equivalent within 12 weeks, or persistent Grade 2 to 3 AEs (unless unequivocally attributed to another cause) that do not recover to Grade 1 or less within 12

Proprietary confidential information © 2021 Boehringer Ingelheim International GmbH or one or more of its affiliated companies

weeks. Study drug(s) should also be permanently discontinued for Grade 3 to 4 AEs that are classified as immune-related by the Investigator that are not listed in Appendix [10.1](#). Study drug(s) should be permanently discontinued if \geq Grade 4 drug-related AEs are reported. Please see Appendix [10.2](#) for guidelines for management of immune-related adverse events.

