5.2.7.5.2 Immune-related adverse events (irAEs)

Immune-related AEs are AEs associated with immunotherapy treatments that appear to be associated with the immune therapy’s mechanism of action. These adverse reactions, which can be severe, may involve the gastrointestinal, skin, liver, endocrine, respiratory, renal, or other organ systems. The sponsor has defined a list of irAEs in [Table 10.1: 1](#) that must be reported as AESIs. All immune-related events are to be reported as AEs. Some irAEs also need to be reported as AESIs as defined by the sponsor in [Table 10.1: 1](#). If an Investigator determines a Grade 3 event (not on the list) to be immune-related, the Investigator should also report that event as an AESI.

Recommendations for the management of irAEs are presented in Appendix [10.2](#).

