5.2.7.8 Adverse event collection and reporting

5.2.7.8.1 AE Collection

The investigator shall maintain and keep detailed records of all AEs in the patient files.

The following must be collected and documented on the appropriate CRF(s) by the investigator:

- From signing the informed consent onwards until the end of the 30-day safety follow-up visit
 - all AEs (non-serious and serious) and all AESIs.
- After the 30-day safety follow-up visit until the individual patient's end of trial:
 - all related SAEs and all related AESIs.
- After the individual patient's end of the trial:
the investigator does not need to actively monitor the patient for AEs but should report related SAEs and related AESIs of which the investigator may become aware of by any means of communication, e.g. phone call. Those AEs should however, not be reported in the CRF.

The rules for Adverse Event Reporting exemptions still apply.

[figure not shown]

Figure 5.2.7.8.1: 1 Safety follow-up schema

AE reporting to sponsor and timelines

The investigator must report SAEs, AESIs, and non-serious AEs which are relevant for the reported SAE or AESI, on the BI SAE form via fax immediately (within 24 hours) to the sponsor's unique entry point (country specific contact details will be provided in the ISF). The same timeline applies if follow-up information becomes available. In specific occasions the investigator could inform the sponsor upfront via telephone. This does not replace the requirement to complete and fax the BI SAE form.

With receipt of any further information to these events, a follow-up SAE form has to be provided. For follow-up information the same rules and timeline apply as for initial information.

Information required

For each AE, the investigator should provide the information requested on the appropriate eCRF pages and the BI SAE form, if applicable. The investigator should determine the causal relationship to the trial medication.

The following should also be recorded as an (S)AE in the CRF and BI SAE form (if applicable):

- Worsening of pre-existing conditions other than the underlying disease
- Changes in vital signs, ECG, physical examination and laboratory test results, if they are judged clinically relevant by the investigator

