 - BI 754091 and BI 754111 should be permanently discontinued for any recurrent Grade 3-4 AE, inability to taper steroids to 10 mg or less prednisone or equivalent within 12 weeks, or persistent Grade 2-3 AEs that do not recover to Grade 1 or less within 12 weeks.
- Adrenal insufficiency:
 - BI 754091 and BI 754111 should be permanently discontinued for Grade 3-4 adrenal insufficiency or persistent Grade 2 AEs that do not recover to Grade 1 or less within 12 weeks.
- Rash:
 - BI 754091 and BI 754111 should be permanently discontinued for Grade 4 rash, any recurrent Grade 3 AE or persistent Grade 2-3 AEs that do not recover to Grade 1 or less within 12 weeks.
- Encephalitis:
 - BI 754091 and BI 754111 should be permanently discontinued for any grade encephalitis.
- Infusion reactions:
Signs and symptoms usually develop during or shortly after drug infusion and generally resolve completely within 24 hours of completion of infusion.

10.3 **HANDLING PROCEDURES FOR BLOOD SAMPLES FOR PLASMA CONCENTRATION-TIME MEASUREMENTS**

Handling procedures for blood samples are presented in the Laboratory Manual.

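### Encephalitis ends treatment at any grade but is not on the AESI list, so Grade 1 cases and Grade 2 cases that are not DLTs have no route to AESI status

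*Protocol*

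**What the plan says.** **Discontinuation.** Protocol 4.1.4 includes "any grade encephalitis, Grade 4 hypophysitis, Grade 4 rash" among the events that end study treatment for good. Appendix 10.2 repeats the rule: "BI 754091 and BI 754111 should be permanently discontinued for any grade encephalitis".

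**AESI list.** Appendix 10.1 opens Table 10.1: 1 with "This table defines immune-related AEs that must be reported as AESIs". The row headed "Neurologic (report as AESI for any grade") holds four terms: autoimmune neuropathy, Guillain-Barre syndrome, demyelinating polyneuropathy and myasthenic syndrome. Encephalitis is not among them, and it appears in no other row.

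**Fallback for unlisted events.** The last row of the table adds "Any other Grade 3 event that is considered immune-related by the physician". Section 5.2.7.5.2 says the same: "If an Investigator determines a Grade 3 event (not on the list) to be immune-related, the Investigator should also report that event as an AESI".

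**Other route.** Section 5.2.7.5.1 makes every DLT an AESI, and 4.1.5 defines DLTs and has them recorded throughout the trial.

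**Consequences of AESI status.** AESIs share the 24-hour reporting clock with SAEs (5.2.7.5, 5.2.7.8.1). Up to the 30-day safety follow-up visit every AE is collected. From then to the patient's end of trial, collection narrows to "all related SAEs and all related AESIs". SAP 7.8.1 plans a table of AESIs and a table of irAEs over the whole trial, including those after the residual effect period.

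**The concern.** Encephalitis is the only diagnosis named in 4.1.4 for which any grade, at first occurrence, ends treatment. The protocol describes AESIs as events of particular concern for prospective safety monitoring. One would expect the first list to feed the second, and for every other named diagnosis it does. As written, a Grade 1 myasthenic syndrome goes to the sponsor within 24 hours, while a non-serious Grade 1 encephalitis that stops treatment does not.

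Three things are at stake for the affected cases: prompt notice to the sponsor, a line in the AESI table and, for late onsets, being recorded at all. Notice matters because the enrolment stopping rule in 3.3.4.3.1 looks at the frequency and severity of events such as irAEs.

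**Working it through.** No arithmetic applies. The check sets the lists side by side and then follows encephalitis through them by grade and time of onset.

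**Step 1: the diagnoses named in 4.1.4 against Table 10.1: 1.**

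| Diagnosis | Grade that ends treatment | Grade at which it is an AESI |
|---|---|---|
| Pneumonitis | 3-4 | 2 and above |
| Colitis | 3-4, or any grade if recurrent | 2 and above, or any grade with dose modification or systemic steroids |
| Adrenal insufficiency | 3-4 | 3 and above (2 with dose modification or steroids) |
| Hypophysitis | 4 | 3 and above (2 with dose modification or steroids) |
| Rash | 4 | 3 and above |
| Diabetes mellitus | 4 | Any, for new-onset Type 1 |
| Encephalitis | Any | Not listed |

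In every other row, the grade that ends treatment is already an AESI. For recurrent Grade 1 colitis this assumes that discontinuation counts as a dose modification.

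**Step 2: routes to AESI status for encephalitis.**

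| Case | Route | AESI? |
|---|---|---|
| Grade 1 | None | No |
| Grade 2, not a DLT | None | No |
| Grade 2 that persists and prevents dosing on Cycle 2 Day 1 | DLT (4.1.5), hence AESI (5.2.7.5.1) | Yes |
| Grade 3 | Fallback, if judged immune-related; generally also a DLT | Yes |
| Grade 4-5 | DLT at any time | Yes |

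The gap is the first two rows.

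**Step 3: what happens to those two rows.**

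- *Onset up to the 30-day visit.* The event is recorded as an AE, since 5.2.7.5.2 requires every immune-related event to be reported at least as an AE, and it is followed to resolution or stability (5.2.7.8.1). On-treatment cases appear in the SAP's general AE table and, where they led to discontinuation, in that table; they enter the irAE tables if judged immune-related. They are absent from the AESI table. If non-serious, they carry no 24-hour duty.
- *Onset after the 30-day visit.* Only related SAEs and related AESIs are collected. A non-serious case is neither, so it is not collected and the whole-trial irAE table cannot contain it. The window exists: Part III patients who have not progressed are contacted at least every 12 weeks until progression or another end point (6.2.3.3).
- *Serious cases at any time.* The SAE route gives the 24-hour report and, if related, late collection. Seriousness alone does not add the event to the AESI table.

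**The case against.** The strongest objections are these.

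1. **The DLT route reaches some Grade 2 cases.** A reader might infer that all Grade 1-2 encephalitis falls outside AESI reporting. The documents do not support that: a Cycle 1 case of Grade 2 that persists and prevents dosing on Cycle 2 Day 1 is a DLT and therefore an AESI. This stands, and it sets the scope used here.
2. **The Always Serious list.** Section 5.2.7.4 refers to a sponsor list, kept in the eDC system, of events that must always be reported as SAEs. If encephalitis is on it, every grade has the 24-hour clock, and related late cases are collected. This stands as an unresolved dependency. It would not make the event an AESI, so the AESI table gap would remain.
3. **On-treatment cases are visible elsewhere.** They are collected, the reason for discontinuation goes into the CRF (3.3.4.1), the SMC receives all available safety data (5.2), and other SAP tables show them. This stands: it would be wrong to infer that such cases go unrecorded.
4. **Late non-collection is a general rule.** It applies equally to, for example, Grade 1 pneumonitis, and by then treatment has already stopped. This is true. But any-grade AESI terms such as those in the neurologic row are exempt from it when related, and encephalitis is not.
5. **No rule ties the two lists together.** Guillain-Barre syndrome and myocarditis are any-grade AESIs without being named in 4.1.4, and persistent Grade 2-3 AEs end treatment without being AESIs as such. So this is a mismatch, not a breach. A reader might also infer that the protocol ranks encephalitis as its least tolerable event; it states no such ranking.

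**Conclusion.** The point holds in a limited form and is minor. Two groups have no AESI route: Grade 1 encephalitis at any time, and Grade 2 encephalitis that does not meet the DLT criterion. On-treatment cases in these groups are missing from the AESI table whether or not they are serious. If non-serious, they also have no 24-hour report. New non-serious onsets after the 30-day visit are not collected.

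The AESI table gap rests only on the text of the two documents. The other two gaps assume that encephalitis is not on the Always Serious list, which cannot be checked here. The documents give no rate for encephalitis, so the number of affected patients cannot be estimated; few are expected. No primary or secondary endpoint analysis is affected, and DLT counts for the MTD do not depend on AESI status.

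The omission looks unintended. The colitis, haematologic, hepatic and ocular rows already treat a dose modification at any grade as a trigger, and an event that always stops dosing fits that logic.

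**What to change.** Reconcile Table 10.1: 1 with 4.1.4 and Appendix 10.2 by adding encephalitis to the neurologic row, which already applies at any grade, and carry the term into the AESI specification used for the SAP table. Related cases of every grade would then have the 24-hour report and be collected to the patient's end of trial, and on-treatment cases would enter the AESI table.

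If the sponsor left the term out on purpose, a sentence giving the reason, and saying whether the Always Serious list covers encephalitis, would settle the matter.

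The cost is one line in the table and one term in the specification, with negligible added reporting. No dosing or discontinuation rule changes.
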